3. STUDY DESIGN

3.1 Description of the study

This is a prospective, longitudinal cohort study of a 6-week clinical intervention with Chinese herbs in advanced (Stage 4) NSCLC patients at the Peter Brojde Lung Cancer Centre of the Jewish General Hospital in Montreal. All the active patients who have histologically or cytologically proven metastatic NSCLC with ECOG performance status of 0 -2 will be eligible to participate in the study.

3.2 Sample size

15 patients with advanced non- small- cell- lung cancer will be recruited over a 12- month period at a rate of 1-2 patients per month to receive CH plus standard care. We intend to approach 80 patients from a pool of 200 active advanced NSCLC patients who meet eligibility criteria. Estimated length of the study would be about 18 months.

4. MATERIALS AND METHODS

4.1 Patients

Patients may be screened if they have locally advanced or metastatic NSCLC (per the Union Internationale Contre le Cancer [UICC]/American Joint Committee on Cancer [AJCC] staging system)

4.2 Inclusion Criteria

1. Age 18 years or older
2. Diagnosis of advanced or metastatic NSCLC

3. Stages 4
4. ECOG performance 0-2
5. Life expectancy greater than \geq 3 months
6. No planned chemotherapy within the next 6 weeks or completed at least 1 cycle of current standard chemotherapy and clinically stable.

4.3 Exclusion Criteria

1. Receiving TKI (Tarceva, Iressa)
2. Brain metastases
3. Patients or families who do not speak English or French
4. Abnormal liver function: Alanine aminotransaminase (ALT) $>$ 40 U/L, Aspartate aminotransaminase (AST) $>$ 55 U/L, Alkaline phosphatase (ALP) $>$ 145 U/L, Bilirubin $>$ 1.7 umol/L.
5. Taking regular anti-convulsants, Coumadin or related anti-coagulant, lithium
6. Taking regular immunosuppressive medications: azathioprine (Imuran), basiliximab (Simulect), cyclosporine (Neoral, Sandimmune), daclizumab (Zenapax), muromonab-CD3 (OKT3, Orthoclone OKT3), mycophenolate (CellCept), tacrolimus (FK506, Prograf), sirolimus (Rapamune)
7. Pregnancy

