All the components of the modified **Shu Yu Wan in this protocol** have been approved by Health Canada and listed as acceptable medical ingredients[71, 72], and were the subject of in-depth analysis process as part of a prior CIHR grant application to determine efficacy and safety of CH in cancer patients [73]. Although some mild side effects have been reported when single herbs from the **Shu Yu Wan formula** have been used in doses far exceeding that in our formula, none of the component of this formula are listed as a herbals to be used with caution in *Herb Contraindications and Drug Interactions, 4th edition*[74]. Furthermore most of the ingredients have a high therapeutic index and are unlikely to cause toxicity even used in considerable excess. In general, use of combinations of smaller quantities of herbs seems to cause fewer adverse reactions than larger doses of single herbs, and

combining 23 herbs in one formula allows the use of smaller doses of herbs with synergistic beneficial effects.

More details of individual potential herbal-drug interactions of the components the modified Shu Yu Wan formula is presented in the Appendix 3. It should be noted that most of the data on toxicities reported here come from studies cited in Chinese Herbology textbooks [75].

The closely related modified Shu Yu Wan formula used in another study of advanced lung cancer patient receiving chemotherapy led to significantly fewer adverse reaction when compared to chemotherapy alone [49]. However we note that most of the herbs are metabolized in the liver and that there is potential for reversible hepatotoxicity at high doses or in susceptible patients [76]. This general point will be taken into account in patient selection for the current study. Thus, we propose to exclude patients with abnormal liver function or those taking drugs with long half-lives namely anti-convulsants, anticoagulants, or lithium where minor changes in drug metabolism may lead to delayed and potentially serious sequelae.

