2. OBJECTIVES

2.1 Primary objectives:

- To assess the acceptability and feasibility of conducting a 6-week intervention with a standard CH formula designed to treat symptoms commonly experienced by patients with advanced NSCLC.

Acceptability will be assessed using the following questions at the end of the study:

- **Indirectly** from adherence and feasibility (see below)
- **Directly** from responses to the following questions:
 - i) “*Was the Chinese Herb treatment used in this study easy to take?*” Yes / No
 - ii) “*If you experienced any problems or side effects taking the Chinese Herb treatment used in this study, please tell us what these were.*” (Free text)
 - iii) “*If it was available, would you be willing to take the Chinese Herb treatment used in this study again?*” Yes / No / Don’t know

Feasibility will be assessed using the following indices:

- Willingness to participate: proportion of subjects enrolled from number of patients approached .
- Completion rates: proportion of enrolled subjects who completed study (including final assessment) (threshold for positive study: 60%)
- Adherence rates: Proportion of doses taken of number prescribed (threshold for positive study: 66%)

2.2 Secondary objectives:

- a) Assess the magnitude of the patients' quality of life response and symptoms change after the 6 -week intervention compared to baseline.
- b) Estimate an appropriate sample size for the fully implemented study

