4.4 Method of Treatment

After written informed consent has been obtained and eligibility has been established the patient will be asked to complete FACT-L and ESAS questionnaires. The patients will be offered the choice of taking the CH formula in capsules or sachets and given instructions about recommendations to improve palatability. The formula should be taken with meals 3 times a day (each dose is either 1 sachet or 4 capsules) for six-weeks. Patient will be instructed to complete a diary each day to confirm adherence to treatment and to indicate the reason(s) that any doses were missed or treatment was stopped. A two-week supply of the CH capsules/sachets will be dispensed to patient at the start of the study. Every two weeks thereafter diaries will be collected/checked with the patient and a new diary dispensed with the next two-week supply of formula. The written instructions about dosage, frequency, dosage timing and what to do in the event of an adverse reaction will be given to patients.

Study of Chinese herbs and lung cancer patients

Principal Investigator: [name]

Patients will be allowed to maintain their concomitant medications during the trial with exception of over-the-counter herbal supplements.

4.5 Withdrawal.

Patients may withdraw at any time during the trial for the following reasons:

1. Patient no longer wishes to participate
2. The patient's doctor makes the decision to withdraw the patient if any side effects are suspected.
3. An allergic response or adverse reaction to the Chinese herbs
4. A change in clinical status necessitating emergency admission for treatment
5. Evidence of worsening liver function or need to start medication included in the exclusion criteria.
6. Reduction of chemotherapy dose due to Grade 3 toxicity

In case if participation terminated prematurely, patient will still be asked to attend for the end of the study visit.

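### The bilirubin exclusion limit of 1.7 umol/L appears to carry a wrong figure or unit: read literally, it would exclude most patients whose bilirubin is normal.

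*Protocol*

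**What the plan says.** Section 4.3, item 4, opens with "Abnormal liver function: Alanine aminotransaminase (ALT) $>$ 40 U/L", adds limits of 55 U/L for AST and 145 U/L for ALP, and ends with "Bilirubin $>$ 1.7 umol/L". Section 1.4 gives the reason: most of the herbs are metabolised in the liver and might harm it, so "we propose to exclude patients with abnormal liver function". Bilirubin is mentioned nowhere else in the protocol or SAP.

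Three other places bear on the consequence:

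- Section 3.2 sets a target of 15 patients and states: "We intend to approach 80 patients from a pool of 200 active advanced NSCLC patients who meet eligibility criteria".
- Section 2.1 lists among the feasibility indices "Willingness to participate: proportion of subjects enrolled from number of patients approached".
- Section 4.4 begins the treatment sequence with "After written informed consent has been obtained and eligibility has been established". Table 3 places consent and a standard-of-care blood test at the same screening visit.

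**The concern.** The item is meant to remove patients with abnormal liver function. A bilirubin limit far below the top of the normal range does the opposite of what its heading says, because it removes people whose result is normal.

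Two things would follow from literal use. Recruitment would suffer severely. And one primary feasibility index could mislead: patients who are approached, agree, and are then excluded on bilirubin stay in the denominator of enrolled over approached, so they look unwilling although they did not refuse. If staff instead apply a sensible but unwritten value, most enrolments would breach the written criterion.

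**Working it through.** **Inputs from the protocol.** Limit 1.7 umol/L (Section 4.3); 15 to enrol, 80 to approach, pool of 200 (Section 3.2). The plan does not derive the limit, so there is no calculation of its own to reproduce.

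**Assumptions, not from the documents.** Upper limit of normal U = 17-21 umol/L; lower limit L = 0.5-5 umol/L; 1 mg/dL = about 17.1 umol/L.

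**Step 1: ratio to the upper limit.** 1.7/17 = 10.0% and 1.7/21 = 8.1%. With U widened to 15-25, the ratio is 11.3% to 6.8%.

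**Step 2: units.** 1.7/17.1 = 0.099 mg/dL. The same digits read as mg/dL would be 1.7 x 17.1 = about 29 umol/L. A unit slip or a decimal slip could each explain the figure; the documents do not show which.

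**Step 3: share of healthy adults above 1.7.** Use a lognormal distribution with its 2.5% and 97.5% points at L and U. The log-scale mean is ln(L x U)/2, the log-scale SD is ln(U/L)/(2 x 1.96), and the share is 1 - Phi[(ln 1.7 - mean)/SD].

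Example, L = 0.5 and U = 17: mean = ln(8.5)/2 = 1.070; SD = ln(34)/3.92 = 0.900; (0.531 - 1.070)/0.900 = -0.60; share = 0.726.

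| L | U = 17 | U = 21 |
|---|---|---|
| 0.5 | 72.6% | 75.1% |
| 1 | 89.0% | 89.9% |
| 1.7 | 97.5% | 97.5% |
| 2 | 98.8% | 98.7% |
| 3 | 99.9% | 99.9% |
| 5 | about 100% | about 100% |

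**Step 4: sensitivity.**

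- With U cut to 10, the share is 64.0% (L = 0.5), 85.5% (L = 1) and 99.1% (L = 2).
- A flat distribution from 0 to U gives 1 - 1.7/17 = 90.0% and 1 - 1.7/21 = 91.9%.
- The lognormal median is the square root of L x U, so half are excluded when L = 1.7 x 1.7/U, which is 0.170 (U = 17) or 0.138 (U = 21). Only below that would fewer than half be excluded.

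**Step 5: effect on recruitment.** The plan implies 15/80 = 18.75% enrolled over approached. If bilirubin is checked after approach and every patient agrees, that ratio cannot exceed the share at or below 1.7:

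| L | Ceiling on enrolled/approached | Out of 80 | Out of 200 |
|---|---|---|---|
| 0.5 | 24.9-27.4% | 20-22 | 50-55 |
| 1 | 10.1-11.0% | 8-9 | 20-22 |
| 2-5 | at most 1.3% | about 1 or fewer | about 3 or fewer |

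At L = 0.5, reaching 15 would need 15/22 = 68% to 15/20 = 75% of those remaining to enrol, before any other exclusion. From L = 1 upward, 80 approaches cannot yield 15.

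**The case against.** The strongest reply is that the documents do not contradict themselves; the case needs an outside reference range. That is true, and the range is labelled as an assumption, but the result survives every upper limit from 10 to 25 umol/L that was tried.

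The criterion does not say total or direct bilirubin. If direct was meant, with an upper limit of about 5 (also an assumption), a flat distribution gives 1 - 1.7/5 = 66% excluded, and a lognormal with limits 0.5 and 5 gives about 45%. This weakens the claim about most normal values on that reading. But the text does not state that reading, and 1.7 would still lie well inside the normal range.

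The willingness argument is conditional. Section 3.2 can be read as approaching only patients already known to be eligible, standard-of-care bloods may be available beforehand, and Section 4.4 names consent and eligibility without clearly fixing their order. Known bloods would protect the index, though not recruitment. The willingness index also has no pass mark, unlike completion (60%) and adherence (66%).

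Nor is the pool of 200 a firm contradiction. The sentence is ambiguous, and Section 3.1 says stage 4 patients "with ECOG performance status of 0 -2 will be eligible to participate in the study", a use of the word that ignores the laboratory exclusions.

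Finally, a text-extraction slip cannot be ruled out. The digits and unit are legible, however, and the three neighbouring limits look intact. The error is also one of over-exclusion: it exposes no additional patient to the herbs and would show at the first screenings. That limits the harm but does not make the criterion usable as written.

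**Conclusion.** The concern holds. As written, the bilirubin limit does not fit its own heading or the stated purpose in Section 1.4. At 8-10% of an assumed upper limit of 17-21 umol/L, it would exclude about 73% to nearly 100% of people with healthy liver function, depending on the lower limit. These shares come from a healthy-adult model, not from patients with advanced lung cancer; the exact percentages matter less than the direction, which holds for every total-bilirubin range examined. The target of 15 from 80 approached would be tight at best and out of reach if the lower limit is 1 or more and bilirubin is checked after approach. The effect on the willingness index depends on that same order of events. Confidence is medium, because the reference range is assumed and the source page has not been seen. It should still be settled before screening, because the trial cannot apply this criterion literally without serious loss of eligible patients.

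**What to change.** 1. Check the source page of Section 4.3 to rule out a text-extraction slip.
2. If the figure stands there, check it and its unit against the site laboratory's reference range, and state whether total or direct bilirubin is meant.
3. Correct whichever is wrong, and reconcile Section 4.3 with the purpose in Section 1.4 and the recruitment pool in Section 3.2.

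No replacement value is offered here; the limit is a matter for the sponsor's clinicians. The cost is a one-line eligibility amendment, with no extra tests or patients. If the source page shows a different figure that fits the laboratory range, no amendment is needed.

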4.4 Method of Treatment

After written informed consent has been obtained and eligibility has been established the patient will be asked to complete FACT-L and ESAS questionnaires. The patients will be offered the choice of taking the CH formula in capsules or sachets and given instructions about recommendations to improve palatability. The formula should be taken with meals 3 times a day (each dose is either 1 sachet or 4 capsules) for six-weeks. Patient will be instructed to complete a diary each day to confirm adherence to treatment and to indicate the reason(s) that any doses were missed or treatment was stopped. A two-week supply of the CH capsules/sachets will be dispensed to patient at the start of the study. Every two weeks thereafter diaries will be collected/checked with the patient and a new diary dispensed with the next two-week supply of formula. The written instructions about dosage, frequency, dosage timing and what to do in the event of an adverse reaction will be given to patients.

Study of Chinese herbs and lung cancer patients

Principal Investigator: [name]

Patients will be allowed to maintain their concomitant medications during the trial with exception of over-the-counter herbal supplements.

4.5 Withdrawal.

Patients may withdraw at any time during the trial for the following reasons:

1. Patient no longer wishes to participate
2. The patient's doctor makes the decision to withdraw the patient if any side effects are suspected.
3. An allergic response or adverse reaction to the Chinese herbs
4. A change in clinical status necessitating emergency admission for treatment
5. Evidence of worsening liver function or need to start medication included in the exclusion criteria.
6. Reduction of chemotherapy dose due to Grade 3 toxicity

In case if participation terminated prematurely, patient will still be asked to attend for the end of the study visit.

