leading to hypertension and hypokalemia [67]; Increased risk of bleeding: dong quai (angelica senesis) at the dose of 4.5 g daily due to antiplatelet activity: concurrent use of anticoagulants is not recommended [68]; Neurological and psychiatric toxicity: Panax ginseng may cause insomnia, mania and/or euphoria when used in a dose >2 g daily over prolonged time (3 months) [69, 70]. The toxicities reported argue for supervised use of CH in clinical studies to monitor symptoms and parameters such as blood pressure.

D. There is genuine difficulty in predicting potential clinically important interactions between CH and other chemicals or biomolecules at physiologically relevant concentrations. This in turn raises the possibility that for patients receiving potentially highly toxic treatments such as chemotherapy, CH may increase the risk of toxicity. Additionally, for patients being treated with curative intent there is potential that any additional treatment such as CH may reduce rather than enhance any anti-cancer effect and jeopardise survival. **Response:** In recent years there has been a rapid increase in the number of published studies using CH in cancer patients, including many studies using CH at the same time as chemotherapy. Not one of these studies has reported an increase in symptoms or adverse effects due to CH despite use in a variety of different patient groups, and many claim that CH enhances rather than reduces anti-cancer treatment effects. This protocol is deliberately designed to test CH in stage IV lung cancer patients, where anti-cancer treatment is intended to reduce or control symptoms and improve quality rather than extend life. To be able to better identify if CH are causing, rather than reducing toxicity for those on chemotherapy, we will start CH only in patients who have no chemotherapy planned or in those starting chemotherapy CH will be initiated only if they are clinically stable and have completed at least the first cycle of chemotherapy. Furthermore, to reduce the potential for other toxicities, patients will be instructed not to take other over-the-counter CH.

1.4 Rationale, composition and safety data for the of the study formula - Shu Yu Wan (Chinese Yam Pill) formula

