The basis for the formula chosen is the “Eight treasure deconcoction” (Protocol Table 2: 1-8) that is used to improve energy and combat fatigue in otherwise healthy individuals. This fundamental formula is represented in the majority of deconcoctions studied in the recent review by Ma et al [ref]. In the context of other diseases the Eight Treasures combination is not thought to be strong enough and the remaining 13 herbs are added for their anticipated supplementary effects in treating symptoms in

the context of lung cancer. These include herbs to help with lung symptoms such as cough (10,11,15) and dry mouth (17), poor appetite and early satiety (13, 14,20, 21), emotional stress (18) and to strengthen the individual's natural defences (12, 19,22,23) in the face of severe illness. The classical Shu Yu Wan formula dates back to the late Han dynasty c. 220 AD and includes 21 herbs. This formula has been used for hundreds of years as a treatment for severe illness-induced fatigue and weakness. However, two of the classical ingredients (Da Dou Huang, Bai Lan) are not approved in the NHPD list and have been substituted with appropriately selected additional herbs that are on NHPD approved list (Table 2:15,20,22,23). In Traditional Chinese Medicine there is considerable scope for individual practitioners to choose different herbs from each botanical family to treat different patients with the same symptom. Interestingly, another group in China has published on a study of their own version of a modified Shu Yu Wan formula [49] and its use for improving QoL for patients with Non-small cell lung cancer. Liang et al's formula included 25 herbs, of which 21 are exactly the same as the ones chosen for the Shu Yu Wan formula selected for our study.

In choosing the CH used in this study, the aim was to identify a balanced combination that would be generally applicable and effective in reducing symptoms for patients with advanced lung cancer. As described above this study will use the modified **Shu Yu Wan** formula with 23 different herbs (Table 2). In addition it was our express intention to include the botanicals that are most likely to improve symptoms and quality of life in patients with advanced lung cancer and not to include botanicals because of any potential anti-cancer activity. In contrast to the usual TCM practice, we will use a standardized formula suitable for all patients, rather than an individualized CH prescription with only selected components.

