5. STUDY TREATMENT

5.1 Chinese herbs Formulation, Packaging, and Handling:

Chinese herbs for study formula (**Shu Yu Wan**) will be imported from Sun Ten Pharmaceutical Company in Taiwan and will be manufactured as a sachets and capsules by BEMA Botanicals distribution company in Vancouver. As described above BEMA have in place processes for certifying sourcing of herbs and verification of absence of contaminants and complies with Health Canada's Good Manufacturing Practices. BEMA will compound the capsules and sachets (<http://www.bemabotanicals.com/>). The signed copy of certificate of analysis (COA) provided by Bema's supplier will be kept with BEMA. The BEMA Botanicals obliged periodically inspect the cultivation site and analyze the samples to ensure they are fresh and not sulfur fumigated.

BEMA's quality assurance department also will keep a copy together with all batch manufacturing records. All the basic testing such as heavy metals, microbiological test, etc. is conducted by SUNTEN's quality assurance department.

Study of Chinese herbs and lung cancer patients
Principal Investigator: [name]

The formula will be shipped in light opaque-white HDPE jars that contain an estimated 500 caps/sachets to the Peter Brojde Lung Cancer Clinic in Montreal by UPS (about 3 days), and stored at room temperature.

Table 2 Study formula - Shu Yu Wan (*Chinese Yam Pill*)

	Ingredients	Ratio	Percent	Daily dose (mg)
1	RenShen (Radix et Rizoma Ginseng)	7	3.5%	350
2	Bai Zhu (Rhizoma Atractylodis)	6	3.0%	300
3	Fu Ling (Poriae)	5	2.5%	250
4	Zhi Gan Cao (Radix GlycyrrhizaPreparata)	20	10.0%	1000
5	Shu Di Huang (Rehmannia glutinosa)	10	5.0%	500
6	Bai Shao (Radix Paeoniae Alba)	6	3.0%	300
7	Dang Gui (Radix Angelica sinensis)	10	5.0%	500
8	ChuanXiong (Rhizoma Chuang xiong)	6	3.0%	300
9	Gui Zhi (Ramulus Cinnamomum)	10	5.0%	500
10	Xing Ren (Semen armeniaca amarum)	6	3.0%	300
11	JieGeng (RadixPlatycodonis)	5	2.5%	250
12	Fang Feng (Radix Saponikoviae)	6	3.0%	300
13	Da Zao (Fructus Jujubae)	5	2.5%	250
14	ShenQu (Massa Medica Fermentata)	10	5.0%	500
15	Dong Chong Xia Cao (Cordyceps)	10	5.0%	500
16	Shan Yao (RhizomaDioscoreae)	30	15.0%	1500
17	Mai Men Dong (Radix Ophiopogonis)	6	3.0%	300

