5.2 Study assessments

Flowcharts of scheduled study assessments are provided in Table 3. Patients will be closely monitored for safety and tolerability throughout the study. At each visit patients will be asked about new or worsening of existing symptoms. The severity of the adverse reaction will be determined by Common Terminology Criteria for Adverse Events (CTC AE) version 3.0. All assessments must be performed and documented for each patient in the CRF.

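### Sections 1.3D and 4.4 bar only over-the-counter herbs, so as worded a practitioner-supplied herbal product may be taken beside the study formula

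*Protocol*

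**What the plan says.** Two sentences in the protocol restrict other herbs. Section 1.3D, on interactions and added toxicity, says: "to reduce the potential for other toxicities, patients will be instructed not to take other over-the-counter CH". Section 4.4 turns this into a treatment rule: "Patients will be allowed to maintain their concomitant medications during the trial with exception of over-the-counter herbal supplements".

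Other parts of the protocol bear on how these sentences work:

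- Section 1.3C, citing community surveys of side effects, explains over-the-counter use as unsupervised use.
- Section 1.4 contrasts the study product with ordinary practice: "In contrast to the usual TCM practice, we will use a standardized formula suitable for all patients, rather than an individualized CH prescription". It also rests part of the safety argument on dose: "combining 23 herbs in one formula allows the use of smaller doses of herbs".
- Section 5.3 includes herbal and homeopathic remedies among the medications recorded for the 7 days before screening. Table 3 has medication checked again at weeks 0, 2, 4 and 6.
- Section 5.2 covers the grading of reactions: "The severity of the adverse reaction will be determined by Common Terminology Criteria for Adverse Events". It gives no rule for assigning cause.

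The SAP says in general terms that data will be summarized descriptively. It does not mention use of other herbs.

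**The concern.** The bar exists to limit toxicity from herbs added to the study formula, but it is defined by the route of supply. A herb from a practitioner carries the same pharmacological risk as one bought from a shop. It also lacks the safeguards that the protocol describes for its own product, namely supplier testing and certificates (section 1.3A and B) and a fixed, low dose of each component (section 1.4).

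Two things are at stake. The first is safety: a second herbal product can add to the study doses without limit and without breaking the protocol. The second is interpretation: withdrawal reason 3 (section 4.5) and acceptability question (ii) (section 2.1) both concern reactions to the study herbs, and a second product makes a reaction harder to place.

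The setting makes this worth closing. Section 1.2 reports informal testimony that at least 12 recent lung cancer patients at this centre used Chinese herbs, most or all without telling their oncologists.

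**Working it through.** The plan gives no figure to reproduce here. The check is whether any rule in the documents reaches a practitioner-supplied herbal product.

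1. **Scope of the bar.** Sections 1.3D and 4.4 both carry the over-the-counter qualifier. With the explanation in section 1.3C, the term means unsupervised use. Herbs prescribed and followed by a practitioner are supervised, so they fall outside it.
2. **Default for everything else.** Section 4.4 lets concomitant medications continue unless they fall under the exception. Section 5.3 treats herbal remedies as medications. A practitioner's herbal product is therefore a medication outside the exception, and may continue.
3. **Inclusion criteria (4.2).** The six items cover age, diagnosis, stage, performance status, life expectancy and chemotherapy timing. None concerns herbs.
4. **Exclusion criteria (4.3).** The drug items name TKIs, anti-convulsants, Coumadin and related anticoagulants, lithium, and immunosuppressants. No herbal product is named and no washout is set.
5. **Withdrawal (4.5).** Reason 5 is triggered by worsening liver function or by needing a drug on the exclusion list, and that list names no herb. Reasons 2 and 3 need a suspected side effect or a reaction. They respond to harm and do not prevent the exposure.
6. **Monitoring.** Vital signs and standard-of-care blood tests at every visit, and INR at weeks 2 and 6, may detect a problem. They do not show which product caused it.
7. **Aim against rule.** The aim in section 1.3D is to reduce other toxicities. Steps 1 to 5 leave one source of herbs outside the rule, and section 1.4 describes individual prescription as usual practice in Traditional Chinese Medicine.

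One piece of arithmetic bears on the cost of closing the gap. Section 3.2 plans 15 patients from 80 approached, so willingness to participate would be 15/80 = 18.75%. If one herb user declined and the number approached stayed at 80, it would be 14/80 = 17.5%, a fall of 1.25 percentage points. If one more patient were approached to keep 15, it would be 15/81 = 18.5%. Section 2.1 sets no threshold for this index.

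**The case against.** **The intent may have been a full bar.** Section 1.3 goes on to argue for supervised use of herbs in clinical studies. Over-the-counter could therefore be read as anything taken outside study supervision. That reading is possible, but the text does not say it, and a patient or coordinator would not naturally class a practitioner's prescription as over-the-counter. The written patient instructions are not in the copy reviewed and may be broader. If so, the protocol should be brought into line with them.

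**Exposure is hypothetical.** Section 1.2 does not say where the local users obtained their herbs, and section 1.4 explains the choice of a standard formula without reporting what patients at the site take. This stands, and no frequency is claimed.

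**Attribution is uncertain anyway.** All patients have stage 4 disease, some will be on chemotherapy, and there is no control arm. The doctor can withdraw a patient on suspicion alone. This also stands: closing the gap removes one source of doubt among several.

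**Stronger readings.** A reader might infer three further things that the documents do not support:

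- *That nothing acts on recorded herb use.* Section 4.4 disallows over-the-counter herbs, and the medication checks are how staff would find them.
- *That the doses in section 1.3C show how much room a second product has.* Any such margin rests on an undocumented product and an unstated dose basis. The bleeding caution for Dang Gui advises against concurrent anticoagulants, and section 4.3 already excludes Coumadin and related agents. The ginseng caution is for three months' use, against six weeks here. For licorice the formula alone gives 1000 mg a day (Table 2), above the 600 mg example, so a remaining margin has no meaning.
- *That a rate of formula-related reactions, with an interval, is compromised.* Neither section 2 nor the SAP names such an outcome.

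**Conclusion.** The gap is real but narrow. As worded, sections 1.3D and 4.4 leave a practitioner-supplied herbal product permitted beside the study formula, against the bar's own aim, and no criterion in sections 4.2, 4.3 or 4.5 closes it. It is a safety wording point with a modest bearing on how reactions are interpreted.

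The number of patients affected cannot be derived from the documents. The effect on the primary feasibility indices is small. A reader might also infer a bias in the FACT-L or ESAS change under objective 2.2(a). The documents give no basis for its size or direction, and showing that change with and without herb users among 15 patients would tell little.

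The conclusion assumes that over-the-counter carries the meaning given in section 1.3C, and that no unseen patient instruction overrides section 4.4.

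**What to change.** 1. Reword sections 1.3D and 4.4 to bar all non-study herbal products, whatever the source, from consent through week 6.
2. Add one line to the SAP: list any non-study herb use recorded under section 5.3 and Table 3 beside that patient's adverse reactions.

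The cost is wording in two protocol sections and one SAP line. The data are already collected, so no extra visit, test or form is needed. A few herb users may decline to take part. Both the bar and the listing depend on patients saying what they take, which section 1.2 suggests many do not volunteer.
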